### 11.3. Documentation and reporting of Pericardial Events

Since pericardial abnormalities (e.g., pericarditis, pericardial effusion and hemodynamic compromise) exist along a continuum with overlap between the clinical symptomatology and diagnoses, each pericardial AE (including grading of severity for each individual event) along the continuum should be captured separately (Table 11-1).

Table 11-1. Defin	Table 11-1. Definitions of Pericardial Events			
Event Term	Definition	Characteristics/Diagnosis		
Pericarditis	Inflammation of the pericardium	The major clinical manifestations of acute pericarditis include: 1) chest pain, 2) pericardial friction rub, 3) ECG changes (with new widespread ST elevation or PR depressions), and 4) pericardial effusion. At least 2 of these features are usually considered necessary to make the diagnosis.		
Pericardial effusion	Excess exudate, or fluid, in the pericardium	Once a pericardial effusion is suspected, the diagnostic approach consists of 3 steps: 1) establish the presence of effusion, 2) assess the hemodynamic impact, and 3) establish the cause. Clinical evaluation and ECG findings may suggest the presence of a pericardial effusion, but imaging, usually ECHO, is required to establish a diagnosis.		
Hemodynamic Compromise	Mechanical compression of the heart by large amounts of fluid or blood within the pericardial space that limits the normal range of motion and function of the heart	The diagnosis of hemodynamic compromise is based upon clinical and imaging evidence. The following physical findings 1) sinus tachycardia, 2) elevated jugular venous pressure, and 3) pulsus paradoxus are suggestive of frank tamponade. ECHO or other imaging of the pericardium is essential to the diagnosis of hemodynamic compromise.		

All pericardial findings, regardless of seriousness and relationship to study medication, should be reported to the IRB/PB and MethylGene/Mirati. When reporting pericardial events, available ECHO results/reports (or other means of diagnosis if available) should also be provided. All cardiac events, including pericardial findings will be reported to the DSMB to facilitate their ongoing evaluation of safety in subjects treated in this study. Serious pericardial AEs are to be reported according to the standard procedure for reporting of SAEs.

### 11.4. Pregnancies

To ensure patient safety, each pregnancy occurring while the patient is on study treatment must be reported to the IRB/PB and MethylGene/Mirati within 24 hours of learning of its occurrence. The pregnancy should be followed up to determine outcome, including spontaneous or voluntary termination, details of the birth, and the presence or absence of any birth defects, congenital abnormalities, or maternal and/or newborn complications.

Pregnancy should be recorded on a Clinical Trial Pregnancy Form and reported by the investigator to the oncology MethylGene/Mirati Drug Safety and Epidemiology Department (DS&E). Pregnancy follow-up should be recorded on the same form and should include an assessment of the possible relationship to the MethylGene/Mirati study treatment of any pregnancy outcome. Any SAE experienced during pregnancy must be reported on the SAE Report Form.

# 12.0 CRITERIA FOR THERAPEUTIC RESPONSE/OUTCOME ASSESSMENT

The objective of this study is to determine the efficacy of mocetinostat in selected patients with CREBBP/EP300 mutations with DLBCL and FL. The primary efficacy endpoint is the overall

response rate at 1 year, defined as the proportion of patients with a best overall response of CR or PR according to Cheson criteria per Section 12.1. Secondary efficacy endpoints are duration of response and event free survival. Duration of response is defined as the time from the date of first occurrence of CR or PR whichever is recorded first to the date of the first objectively documented progressive disease (PD) or death due to any cause. Event free survival (EFS) is defined as the time from the date of treatment start to the date of the first documented progressive disease (PD) or death due to any cause.

### 12.1. Criteria for evaluation of response

Response will be evaluated, using modified criteria for malignant lymphoma [45]. Response criteria will generally follow the CT scan recommendations as per the revised response criteria for malignant lymphoma [45]. Further clarification on these criteria has been published by [46]. MRI will be allowed only in those cases when CT scan cannot be performed.

Clinical evaluation and tumor assessments will be performed periodically, as is indicated in Table 10-1, based on physical examination, radiological evaluation and core bone marrow biopsy (only to confirm complete responses in patients with bone marrow tumor involvement prior to study treatment). Clinical suspicion of disease progression at any time will require a physical examination and radiological confirmation to be performed promptly, rather than waiting for the next scheduled tumor assessment. In case of an unscheduled or delayed tumor assessment for any reason, subsequent tumor assessments must be performed according to the originally planned schedule from baseline.

#### 12.1. Measurability of lesion for objective response

- Measurable disease: lesions that can be accurately measured in two dimensions by CT, MRI, plain x-ray of other conventional technique and have a greatest transverse diameter of 2 cm or greater. Splenomegaly alone is not sufficient to qualify as measurable disease. PET scans alone are insufficient for evaluation of measurable disease.
- Non-measurable disease: All other lesions including unidimensional lesions, lesions too small to be considered measurable, pleural or pericardial effusions, ascites, bone disease, leptomeningeal disease, lymphangitis, pulmonitis, abdominal masses not confirmed by CT of disease documented only by indirect evidence (e.g. lab values).

#### 12.2. Objective disease response assessment

Objective status is to be recorded at each evaluation according to the 2007 revised Cheson criteria [45]. All measurable lesions up to a maximum of 6 lesions (largest) should be identified as target lesions at baseline. If there are more than 6 measurable lesions, the remaining will be identified as non-target lesions and included as non-measurable disease. The 6 lesions should be selected according to the following features: they should be from disparate regions of the body and they should include mediastinal and retroperitoneal areas of disease if these sites have measurable lesions. Measurements must be provided for target lesions, while presence or absence must be noted for non-target measurable and non-measurable lesions.

- Complete response (CR): Complete disappearance of all measurable and non-measurable disease with the exception of the following. In patients with positive PET prior to therapy, a post treatment residual mass of any size is permitted as long as it is PET negative. If the PET scan was negative prior to therapy, all nodal masses > 2 cm in greatest transverse diameter (GTD) at baseline must have regressed to ≤ 2 cm in GTD and all nodal masses > 1 cm and ≤ 2 cm in GTD and > 1 cm in their short axis before treatment must have regressed to ≤ 1 cm in their short axis. No new lymphoma lesions should be visible on PET scan or by any other imaging studies. The spleen and/or liver, if considered enlarged at baseline based on physical examination or imaging study (other than PET), must have regressed in size and must not be palpable. If bone marrow was positive at baseline, it must be negative based on biopsy and aspirate at the same site. Normalization of markers (i.e. LDH) definitely assignable to DLBCL or FL. Tumor measurements must be obtained by an imaging modality other than PET. All disease must be assessed using the same technique as baseline unless clinically contraindicated.
- Partial response (PR): Applies to patients with at least one lesion that does not qualify for a CR. For patients with measurable disease, ≥ 50% decrease in sum of the product of the diameters (SPD) of up to 6 dominant lesions identified at baseline. No new lesions and in increase in the size of extranodal disease. Extranodal disease (splenic and hepatic lesions) must have regressed by ≥ 50% in SPD. In patients with a positive PET scan prior to therapy, PET should be positive in at least one previously involved site. Tumor measurements must be obtained by an imaging modality other than PET. All disease must be assessed using the same technique as baseline unless clinically contraindicated. Patients who meet all other criteria but have new lesions observed on PET scan only (not confirmed on CT or other imaging studies) are considered partial responders.
- Stable disease (SD): Does not qualify for CR, PR, or relapsed/progressive disease. Tumor measurements must be obtained by an imaging modality other than PET. Persistent abnormalities seen on CT scans must be FDG-avid on PET scans. All disease must be assessed using the same technique as baseline unless clinically contraindicated.
- Relapsed disease (after CR)/Progressive disease (after PR or SD): At least 50% increase in the SPD of target measurable nodal lesions over the smallest sum observed (over baseline if no decrease during therapy), or ≥ 50% increase in the GTD of any node > 1 cm in shortest axis, or ≥ 50% increase in the SPD of other target measurable lesions (e.g. splenic or hepatic nodules) over the smallest sum observed. Appearance of any new bone marrow involvement. Appearance of any new lesion > 2 cm in longest axis, or ≥ 50% increase in GTD of any previously involved node with a diameter ≤ 1 cm in the short axis such that its longest axis is not > 2 cm. Lymph nodes should be considered abnormal for relapse or progressive disease only if the long axis is > 2 cm, or if both the long and short axis are > 1 cm. In patients with a positive PET scan before therapy, lesions should be PET positive. Tumor measurements must be obtained by an imaging modality other than PET and preferably consistent throughout the study unless clinically contraindicated. Appearance of any new lesion on PET alone (not confirmed by CT or other imaging modality) is NOT considered relapse or progression.

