### 14.0 BIOSTATISTICS

The primary objective is to determine the efficacy of Mocetinostat in patients with relapsed/refractory DLBCL and FL who have inactivating mutations of acetyltransferase genes. To this end we will examine the endpoint of 1-yr overall response (complete response or partial response defined as per Cheson criteria further elaborated in Section 12.1). Currently this rate is around 15% for both lymphoma subtypes based on a previous study [2], and we expect to improve it to 40%. To this end we will use two parallel optimal Simon two-stage designs, one for each subtype, to test the rate of 15% (lower than which will be unacceptable) vs 40% (higher than which will be acceptable). For each subtype, in the first stage, we will enroll 10 eligible patients. If 1 or 0 patients show response in a year, no additional patients will be enrolled and the regimen will be considered not promising. If 2 or more patients show response, then an additional 15 patients will be enrolled for the second stage. Among the 25 patients, If 7 or more patients are able to show response then this treatment regimen will be declared effective. For this decision rule the type I error (declare Mocetinostat promising while it is actually not) rate is 6% and the type II error (declare Mocetinostat not promising while it actually is) rate is around 10%. The early stopping (i.e., stop after the first stage with 10 patients) probability is 0.54 when the true response rate is 15% or lower, and is 0.046 when the response rate is 45% or higher. If a patient died or progressed (and consequently received other treatments) within a year before showing any responses, or provided no information about the best response status, he/she will be recorded as a non-respondent patient. We expect the withdrawal/drop-out rate to be low (around 10%). However if such events occurred due to reasons unrelated with the disease and the patients had not shown any sign of response or progression, such patients will be replaced by new patients.

Due to the potential withdrawal we will enroll totally 56 patients (28 each subtype), and we expect to have 50 analyzable patients (25 each subtype) within 4 years. Note that only the first 25 analyzable patients, for each lymphoma subtype, will be counted towards the analysis of primary objective. For other objectives, all available patients will be used and the analysis will be done separately for each subtype.

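### Section 12.2 ties partial response to residual PET activity, so a PET-negative patient with at least 50% shrinkage who misses CR on marrow, assignable LDH or spleen/liver is not a responder at that visit

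*Combined protocol and SAP*

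**What the plan says.** The primary endpoint (Section 12.0) is the proportion of patients whose best overall response is CR or PR. Section 12.2 defines the categories.

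- **CR.** With a positive baseline PET, "a post treatment residual mass of any size is permitted as long as it is PET negative". CR has further conditions. On marrow: "If bone marrow was positive at baseline, it must be negative based on biopsy and aspirate at the same site". On markers: "Normalization of markers (i.e. LDH) definitely assignable to DLBCL or FL". A spleen or liver that was enlarged at baseline "must have regressed in size and must not be palpable".
- **PR.** The SPD of up to six dominant lesions must fall by at least 50%, and splenic and hepatic lesions must shrink by the same proportion. For the patients at issue, "In patients with a positive PET scan prior to therapy, PET should be positive in at least one previously involved site".
- **Stable disease (SD).** This opens as a catch-all for anyone who is not CR, PR or progressive. It then adds: "Persistent abnormalities seen on CT scans must be FDG-avid on PET scans".
- **Progression (PD).** This needs growth or new disease, and lesions should be PET-positive if the baseline PET was positive.

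Section 12.3 takes best response over all assessments: one CR before relapse, or one PR before progression, is enough. Its response-unknown category covers only progression later than 12 weeks after registration. Section 14.0 says that a patient who "provided no information about the best response status, he/she will be recorded as a non-respondent patient".

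**The concern.** A better PET result should not remove a response. As written, it can. A patient with at least 50% shrinkage and one PET-positive site is PR. If that site also clears while the marrow remains involved, the patient leaves PR without entering CR. No sentence in Sections 10, 12 or 14 assigns this patient to PR.

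Each cohort is decided on small counts: at least 2 responders of 10 to continue, and at least 7 of 25 to declare the drug effective. One reclassified patient can therefore change a cohort's result. Response is assessed by investigators in an open-label, single-arm trial, so a category left to judgment could also be scored differently by different assessors.

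**Working it through.** **Step 1. Apply the definitions to one visit.** The patient was PET-positive at baseline and is now PET-negative at every site. SPD is down at least 50%, any splenic or hepatic lesions have shrunk as PR requires, and there is no new lesion.

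| CR condition missed | CT at this visit | CR | PR | PD | SD |
|---|---|---|---|---|---|
| none | residual mass or clear | yes | – | – | – |
| marrow still involved | clear | no | no (PET clause) | no | yes, by the catch-all |
| marrow still involved | residual mass | no | no | no | catch-all says yes; FDG-avidity sentence arguably says no |
| assignable LDH not normal | clear | no | no | no | yes, by the catch-all |
| assignable LDH not normal | residual mass | no | no | no | as above, disputed |
| spleen or liver still enlarged and palpable | organ abnormal on CT | no | no | no | as above, disputed |

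Whenever a CR condition is missed, the visit is neither CR nor PR. Whether the label is SD or no category depends on how the FDG-avidity sentence is read, but neither is a response.

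**Step 2. From visit to endpoint.** Scans are every 8 weeks for 6 months, then every 12 weeks to one year (Section 10.2). Under Section 12.3 the patient still counts if any other visit is PR with residual PET activity, or if CR is completed later. A response is lost only if neither happens. An example is a patient who is already PET-negative at the first on-treatment scan, around week 8, and whose marrow never clears.

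**Step 3. Reproduce the design.** Inputs from Section 14.0: n₁ = 10, stop at 1 or fewer responders; 15 more patients; effective at 7 or more of 25; response rates 15% and 40%.

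P(effective | p) = Σ, x = 2 to 10, of P(X₁ = x | 10, p) × P(X₂ ≥ 7 − x | 15, p)

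P(stop early | p) = (1 − p)¹⁰ + 10p(1 − p)⁹

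- p = 0.15: P(effective) = 0.063 (stated 6%); P(stop early) = 0.197 + 0.347 = 0.544 (stated 0.54).
- p = 0.40: P(effective) = 0.900 (stated type II error around 10%).

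The plan's error rates reproduce.

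**Step 4. Size, under an assumption.** Let m be the share of true responders lost because they are never scored PR or CR. The documents give no value for m. With a true rate of 40%, the scored rate is 0.40 × (1 − m).

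| m | scored rate | power | wrong stop after stage 1 |
|---|---|---|---|
| 0 | 0.400 | 0.900 | 0.046 |
| 2% | 0.392 | 0.887 | 0.051 |
| 5% | 0.380 | 0.864 | 0.060 |
| 10% | 0.360 | 0.818 | 0.076 |
| 20% | 0.320 | 0.697 | 0.121 |

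At a true rate of 15% the same loss lowers the chance of a false positive. With m = 10% the scored rate is 0.135 and P(effective) is 0.039, against 0.063.

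**The case against.** Much of the case on the other side stands.

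- **Best response needs one qualifying visit.** This stands, and it narrows the effect to patients who are never PR or CR at any visit.
- **The PET clause says should, while neighbouring sentences say must.** Section 12.1 also says that response generally follows the CT recommendations, and Section 12.2 cites the 2007 criteria. An assessor could therefore call PR. That is discretion, not a rule, and nothing says the cited source overrides the written definitions. That source was not available for this review.
- **SD is a catch-all.** A reader might infer that the patient fits no category at all. That holds only if the FDG-avidity sentence is read as an exclusion and a PET-negative CT abnormality remains. With a clear CT the patient is SD.
- **Section 14.0 concerns missing information.** A reader might infer that its rule makes this patient a non-responder. The text does not clearly cover someone with complete scans, marrow and laboratory results. The patient is not counted because the visit is not CR or PR, and the missing-information rule is not needed to reach that result.
- **The reach is limited.** Only patients with a positive baseline PET are affected; Section 10.2.2 lets follicular lymphoma be followed by CT alone. LDH counts only when definitely assignable to lymphoma. Section 10.2.3 requires the confirmatory marrow biopsy, so a biopsy not obtained is a protocol deviation and not a gap in the criteria. That section sets a conditional procedure and does not show that marrow disease will be common here.
- **The wording on extranodal disease.** The phrase "No new lesions and in increase in the size of extranodal disease" might be read as making growth part of PR. The next sentence requires at least 50% regression of splenic and hepatic lesions, so this is a clerical slip.

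**Conclusion.** The point holds in limited form. Applied as written, Section 12.2 denies both CR and PR at that visit to a patient whose PET has cleared with at least 50% shrinkage but who misses CR on marrow, assignable LDH or spleen/liver. A worse PET result would give PR. The primary endpoint is affected only for patients with a positive baseline PET who are never PR or CR at another visit.

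The effect runs one way: it lowers the observed response rate, costs power and does not inflate type I error. Its size is unknown. Power of 0.89 at a 2% loss and 0.70 at a 20% loss marks the ends of an assumed range, with a true rate of 40%. It is not a forecast, and given the best-response rule small shares are at least as plausible as large ones. The documents do not support saying that the go/no-go decision is likely to be wrong.

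**What to change.** In Section 12.2:

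1. Make residual PET positivity a description of PR and not a condition for it.
2. Add a rule such as: *A patient who meets the CT criteria for PR and is PET-negative, but does not meet CR because of marrow, assignable LDH, or spleen or liver findings, is PR.*
3. State that the FDG-avidity sentence under SD does not exclude a PET-negative patient with less than 50% SPD decrease who misses CR.
4. As a clerical correction only, change *in increase* to *no increase* in the PR definition.

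The change is to protocol wording and needs no extra scan or procedure. The cost is that some patients with residual marrow, marker or organ findings will count as PR, which the team should accept explicitly. Make the change before responses are scored, so that it cannot appear to be driven by results.

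### In Section 12.2 the small-node progression clause conflicts with the abnormality sentence after it, so some nodes that grow by 50% or more to over 2 cm meet neither single-node clause

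*Combined protocol and SAP*

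**What the plan says.** The relapsed/progressive disease bullet in Section 12.2 offers several routes to progression. Three concern the growth of known nodes:

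- **Sum of products (SPD):** "At least 50% increase in the SPD of target measurable nodal lesions over the smallest sum observed".
- **Larger-node clause:** at least a 50% "increase in the GTD of any node > 1 cm in shortest axis".
- **Small-node clause:** at least a 50% increase in greatest transverse diameter (GTD) of a previously involved node measuring 1 cm or less "in the short axis such that its longest axis is not > 2 cm".

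A limiting sentence follows: nodes count as abnormal for relapse or progression "only if the long axis is > 2 cm, or if both the long and short axis are > 1 cm". There is also a PET condition: "In patients with a positive PET scan before therapy, lesions should be PET positive".

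Three other provisions bear on the point. The section on measurability requires a measurable lesion to "have a greatest transverse diameter of 2 cm or greater". Section 12.2 says of recording: "Measurements must be provided for target lesions, while presence or absence must be noted for non-target measurable and non-measurable lesions". It also names a governing standard: "Objective status is to be recorded at each evaluation according to the 2007 revised" criteria. Sections 10.2 and 12.1, however, describe the criteria as modified and as following the CT recommendations only in general terms.

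Sections 12.0 and 14.0 end both event free survival and duration of response at documented progression or death from any cause, and Section 14.0 estimates both by Kaplan-Meier.

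**The concern.** The small-node clause requires a long axis of 2 cm or less. For a node whose short axis is still 1 cm or less, the limiting sentence requires a long axis above 2 cm. Read on the same scan, the first test admits only nodes that the second rejects. Nodes that the second would accept can fall outside both single-node clauses.

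What is at stake is the date of progression. Two assessors could apply the same bullet to the same scans and date progression differently, or one of them not at all. Each subtype has at most 28 patients, and duration of response is estimated in responders only, so few events would shape each curve.

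**Working it through.** **Assumptions.** GTD is taken as the long axis. The limiting sentence is taken as a necessary condition. Any PET condition is taken as met. Sizes are short x long axis in cm, and all node sizes are illustrations, not trial data.

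**Step 1: the two sentences side by side.** Suppose the short axis is 1 cm or less on the current scan. The branch of the limiting sentence that needs both axes above 1 cm then fails, which leaves only a long axis above 2 cm. The small-node clause, read on that scan, needs a long axis of 2 cm or less. No node meets both.

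**Step 2: four nodes.** The last two columns say whether a single-node clause is met and the node is abnormal, according to when the 2 cm limit is read.

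| Node | Before | After | GTD change | Abnormal? | Limit read after growth | Limit read before growth |
|---|---|---|---|---|---|---|
| A | 0.8 x 1.2 | 0.9 x 1.8 | 1.8/1.2 = +50% | no | no | no |
| B | 0.8 x 1.5 | 0.9 x 2.4 | 2.4/1.5 = +60% | yes (2.4 > 2) | **no** | yes |
| C | 0.8 x 1.0 | 1.1 x 1.6 | 1.6/1.0 = +60% | yes (both > 1) | yes | yes |
| D | 0.9 x 2.2 | 0.9 x 3.5 | 3.5/2.2 = +59.1% | yes (3.5 > 2) | **no** | **no** |

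A meets the small-node clause but is blocked by the limiting sentence, so its outcome is settled. B depends on the reading. D fails the larger-node clause because its short axis is 0.9 cm throughout, and fails the small-node clause because its long axis exceeds 2 cm both before and after growth. These results do not depend on whether the short axis is read before or after growth, provided both clauses read it at the same time.

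**Step 3: does the SPD clause cover the gap?**

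- A node below 2 cm at baseline, as B is if first seen at 1.5 cm, is not measurable. It cannot be a target and has no SPD route.
- D can be a target. Its product goes from 0.9 x 2.2 = 1.98 to 0.9 x 3.5 = 3.15 cm². As the only target, 3.15/1.98 = +59.1%, which is progression. Beside a stable 2.0 x 2.0 cm target (4.00 cm²), the sum goes from 5.98 to 7.15 cm²; 7.15/5.98 = +19.6%, which is not. The increase of 1.17 cm² reaches 50% only if the smallest sum is at most 1.17/0.5 = 2.34 cm².
- B could be a target that has shrunk. Take 1.6 x 2.0 shrinking to 0.8 x 1.5, with a second target going from 2.0 x 2.0 to 1.0 x 1.0. Baseline sum: 3.20 + 4.00 = 7.20. Smallest sum: 1.20 + 1.00 = 2.20. Regrowth to 0.9 x 2.4: 2.16 + 1.00 = 3.16. Then 3.16/2.20 = +43.6%, below the threshold. This is a miss only if GTD growth is measured from the smallest size, the short axis is read then or currently, and the 2 cm limit is read after growth. From baseline, GTD growth is 2.4/2.0 = +20% and the 50% test fails anyway. With GTD measured from the smallest size but the short axis read at baseline (1.6 cm), the larger-node clause applies. The bullet gives a reference for the SPD increase but none for the GTD increase.

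**Step 4: other routes.** The new-lesion criterion does not reach a previously involved node. The remaining criteria, including new marrow involvement, still apply.

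**The case against.** The strongest reply is that Section 12.2 adopts the 2007 revised criteria, so an assessor would follow that standard rather than an awkward phrase. This has some force, but it does not settle the matter. Sections 10.2 and 12.1 call the criteria modified, so the reader cannot tell a slip from an intended change. The cited source is not among the documents, and an error in text extraction is possible though not shown.

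A second reply is that the 2 cm limit describes the node before growth. That rescues B but not D.

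A third reply is that the gap is narrow, and this stands. It needs growth mainly in the long axis. With proportional 50% growth, any short axis above 1/1.5 = 0.67 cm passes 1 cm, and the larger-node clause catches the node if the short axis is read on the current scan. D must also be a target unless there are more than six measurable lesions, and as sole target it is progression by SPD.

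A reader might infer that progression is delayed by at least one full interval of 8, 12 or 16 weeks. Section 10.2 does not support that. After an unscheduled or delayed scan, patients return to the original schedule, so the next scan may be closer, and clinical suspicion of progression prompts imaging.

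A reader might also infer that the primary result is compromised. Section 12.3 needs only one CR before relapse or one PR before progression, so the clause matters there only before a first response. The Simon boundaries in Section 14.0 do not depend on it.

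**Conclusion.** The inconsistency is real and minor. On the current-scan reading, the small-node clause and the limiting sentence cannot both hold while the short axis is 1 cm or less. B is missed if the 2 cm limit is read after growth; D is missed whether it is read before or after. The SPD clause covers some such nodes and not others.

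The effect is limited to the progression date, and so to the secondary, descriptive event free survival and duration-of-response estimates. Progression could be dated later, up to about the next scheduled scan or beyond, unless another criterion sets the date. The documents give no basis for how often such nodes would occur or for the total effect. The conclusion rests on GTD being the long axis and on the limiting sentence being a necessary condition.

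**What to change.** In the progression bullet of Section 12.2:

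1. Reconcile the small-node clause with the limiting sentence and with the 2007 criteria that the section adopts. Every node meeting the clause should be abnormal under that sentence, and a node with short axis 1 cm or less that grows by 50% or more to over 2 cm long should not be left out.
2. State the reference scan for the GTD increase (baseline or smallest observed) and the scan on which each axis limit is read. Simply deleting *not* is insufficient: with the long axis read after growth, C would be lost if the short axis is read before growth, and kept through the larger-node clause only if it is read after.
3. Require both axes of a growing non-target node to be recorded from scans already done. At present only presence or absence is required, so the 50% test may have no measurement behind it.
4. State whether any departure from the 2007 criteria is intended, and use one version for all response, event free survival and duration-of-response assessments.

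The cost is a wording correction in one bullet, brief clarifying text and some extra data entry. No added scans, procedures or patients are needed.
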